- c See [Table 7.1](#) for safety laboratory details (Virology, Quantiferon Gold® test, and drugs of abuse to be performed at screening only).
- d See [Section 18.0 \(Appendix 2\)](#) for schedule of PK collection time points.
- e See [Section 18.0 \(Appendix 2\)](#) for schedule of peanut challenge assay, biomarker cytokines, and whole blood for leukocytes collection time points. During screening the samples for ex vivo peanut antigen challenge, whole blood for leukocytes, and serum samples for cytokines should be collected prior to administration of BPCFC. If necessary, the sample for ex vivo peanut antigen challenge can be collected on Day 1(instead of Screening), prior to dosing. **Ex vivo Peanut challenge is for Stanford University only.**
- f ET visit will include all procedures to be done at EOS visit as well as any procedures that should be done at the next regularly scheduled visit. ET visit will be performed if the patient discontinues the study before EOS visit. If the patient completes all study visits and return to study center for EOS visit on Day 45, ET visit will not be applicable.
- g Leukocytes will be obtained as part of hematology safety laboratory panel at screening, Day 2, and Day 45/ET. On Day 5 and Day 15, whole blood samples for leukocytes will be collected separately as there is no safety laboratory assessment on Day 5 and Day 15.
- h Only conduct skin prick test and ImmunoCAP testing if these tests had not been performed within 8 weeks before screening.
- i For patients with a history of asthma, spirometry or peak flow will be obtained before starting the initial placebo challenge and again before starting the initial peanut challenge . See [Section 6.1.1](#).
- j Only applicable if the Investigator decides to complete the oral food challenge in 2 days. See [Section 6.1.1](#) and [7.1.3](#) for the instructions to record vital signs, physical examination, and clinical evaluations using the OFC Symptom Scoring Assessment Tool during BPCFC.
- k If the Investigator decides to complete the BPCFC on Day 15, the blood samples for leukocytes (whole blood), biomarker analysis (cytokines), and PK analysis should be collected on the following day (Day 16). The patient's vital signs, adverse events, if any, and concomitant medications will also be recorded on Day 16.

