- l If any objective reaction occurred at Day 14/15, the BPCFC (peanut and placebo oral food challenge) will not be required but may be performed at the discretion of the Investigator
- m The FSH levels will be obtained only on postmenopausal patients defined as aged over 45 years with at least 1 year of amenorrhea. Blood samples to determine the FSH levels will be obtained only at screening.
- n If the Investigator decides to complete the oral food challenge over two days, please refer to Day 46 and appropriate footnotes for guidance.
- o If the BPCFC is continued on Day 46, all assessments related to the BPCFC will be performed on Day 46. Concomitant medications and adverse events will also be recorded on Day 46. All laboratory/diagnostic tests scheduled for the EOS visit will be performed on day 45.
- P If the patient's ET visit is between Day 35 to 45, and the termination is for non-medical reasons, the BPCFC will be administered during the ET visit. If the ET visit is before Day 35, the BPCFC will not be repeated.
- q Informed consent must be obtained prior to participation in the study.

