## 6.0 STUDY PROCEDURES

Study procedures will be performed as detailed in the Schedule of Events in [Table 4.1](#). Assessments scheduled on the day of IP administration must be performed prior to the IP infusion unless otherwise noted. All assessments will be performed on the day of the specified visit; however, a window period of +4 days is available for the Day 14/15 visit. Day 14 and Day 15 visits should remain consecutive. A window period of +/- 2 days can be implemented for visits occurring after completion of the Day 14/15 visit (i.e. Day 45). In addition, the blood sample collected from Stanford University patients for the ex vivo peanut challenge assay scheduled at Screening (prior to OFC), can be collected on Day 1 (prior to IP administration), if necessary.

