### **Criteria for Monitoring and Stopping the Oral Food Challenge**

The Investigator or Sub-Investigator (clinician) should be in the study center during BPCFC.

Monitoring will include recording the vital signs before starting the initial placebo challenge, after completion of the placebo challenge, before starting the initial peanut challenge, upon completion of the final peanut challenge, and 2 hours after completion of the final peanut challenge. (See [Section 7.1.3](#) for more details). A physical examination will be conducted before starting the initial placebo food challenge and upon completion of the final peanut challenge (prior to discharge). For patients with a history of asthma, peak flow or spirometry will be collected before starting the initial placebo challenge and again before starting the initial peanut challenge. The time of dose administration will be recorded. The OFC Symptom Scoring System will be used before starting the initial placebo challenge, after completion of the placebo challenge, before starting the initial peanut challenge, upon completion of the final peanut challenge, and 2 hours after completion of the final peanut challenge.

At the first sign of an objective allergic reaction, the challenge will be stopped and the patient will be immediately assessed and treated accordingly. The EpiPen (1:1000) should be readily available with the patients at the start of the challenge and the Investigator should confirm the availability of other emergency medications and equipment (IV fluid, Benadryl, oxygen, Ambubags, etc.) at the study center. A standard anaphylaxis treatment plan is presented in [Section 16.0 \(Appendix IV\)](#). Any treatments given will be recorded along with the time given and clinical status of the patient. The patient will continue to be assessed and observed as the PI or Sub-Investigator deems appropriate.

A longer observation period may be warranted prior to proceeding with the next dose or discontinuation depending on the patient's clinical status and will be at the judgement of the Investigator.

All patients should have an emergency treatment plan available upon discharge from the study center regardless of the outcome of the study challenge and an EpiPen readily available.

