#### **6.2.5 End of Study**

After the follow-up period, all patients will return to the study center for the EOS visit on Day 45. If any objective reaction occurred at Day 14/15, the BPCFC will not be required but may be performed at the discretion of the Investigator on Day 45 and the symptoms will be monitored (See [Section 6.1.1](#) and [Section 6.1.2](#)). If the Investigator decides to perform the BPCFC, it can be completed in 2 days (one challenge on Day 45 and the second challenge on Day 46) if the Investigator feels that it is the best for patient's safety and convenience. Otherwise all patients will undergo the challenges (peanut challenge and placebo challenge) on Day 45 (EOS visit) itself. All blood samples scheduled for the EOS visit will be collected on Day 45 (EOS visit) regardless of splitting the BPCFC assessments. Additional procedures will be carried out in accordance with the Schedule of Events in [Table 4.1](#).

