#### **6.2.6 Early Termination**

Patients who discontinue the study early will be asked to return to the study center for the ET procedures as shown in the Schedule of Events ([Table 4.1](#)). Patients will only complete the final BPCFC if they discontinue between Day 35 to 45 for non-medical related reasons.

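### The early-termination rule directs a final peanut challenge on Day 35–45 without the exemption that Day 14/15 reactors have at Day 45

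*Protocol*

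**What the plan says.** Two sets of rules in the protocol govern the last food challenge.

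**At the ET visit.** Footnote P of Table 4.1 is the specific rule. For an ET visit between Day 35 and Day 45 it says "and the termination is for non-medical reasons, the BPCFC will be administered during the ET visit". For earlier visits it says "If the ET visit is before Day 35, the BPCFC will not be repeated". Section 6.2.6 covers the same ground in restrictive form: "Patients will only complete the final BPCFC if they discontinue between Day 35 to 45 for non-medical related reasons". Footnote f gives the general rule that the "ET visit will include all procedures to be done at EOS visit".

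**At Day 45.** Footnote l of Table 4.1 says "If any objective reaction occurred at Day 14/15, the BPCFC (peanut and placebo oral food challenge) will not be required" and leaves the decision to the Investigator. Section 6.2.5 says the same: "If any objective reaction occurred at Day 14/15, the BPCFC will not be required but may be performed at the discretion of the Investigator". The synopsis, Section 4.1 and the note to Figure 4.1 agree.

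Neither footnote P nor Section 6.2.6 mentions the outcome of the Day 14/15 challenge.

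**The concern.** Footnote P attaches two conditions to the ET challenge, the timing of the visit and the reason for leaving. When both are met it uses mandatory wording. A patient with an objective reaction at Day 14/15 who leaves on, say, Day 38 for a non-medical reason meets both, so the text directs another peanut challenge. Had the same patient stayed to Day 45, the challenge would have been optional.

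What is at stake is consistency on a safety point. The entry for Amendment 5 in Appendix 3 gives patient safety as the reason for the Day 45 exemption, and that reason applies equally a few days earlier. Footnote P would have a patient who is already leaving the study take a challenge from which the sponsor has released reactors who stay.

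**Working it through.** No figure in the plan needs reproducing. The check compares the rules and then counts the days affected.

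**1. The same patient under each rule.** Take a patient with an objective reaction at Day 14/15.

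| Situation | Governing text | Final challenge |
|---|---|---|
| Attends Day 45 | Footnote l, Section 6.2.5 | Optional, Investigator decides |
| ET on Day 35–45, non-medical | Footnote P | Directed; no exemption stated |
| ET on Day 35–45, medical | Section 6.2.6 | Not done |
| ET before Day 35 | Footnote P, Section 6.2.6 | Not done |

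Only the second row requires a reactor to be challenged. The mandatory wording is in footnote P alone. Section 6.2.6 limits who completes the challenge and does not order it.

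**2. Whether footnote f carries the exemption over.** It brings the End of Study procedures into the ET visit but says nothing about the conditions attached to them. Footnote P is the more specific rule, and it already departs from footnote f by dropping the challenge before Day 35 and limiting it to non-medical terminations. Carry-over therefore has to be inferred.

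**3. Change history (Appendix 3).** Amendment 2 introduced the ET challenge rule, in the Table 4.1 footnote and in Section 6.2.6. Amendment 5 added the exemption later. Of its 9 numbered entries, 5 carry the exemption: synopsis (1b), Section 4.1 (2b), Figure 4.1 (3b), Table 4.1 (4c) and Section 6.2.5 (8a). None is for Section 6.2.6. This is consistent with an oversight but does not prove one.

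**4. Days affected.**
- Span of footnote P, Day 35 to 45 inclusive: 45 − 35 + 1 = 11 days.
- Window for the Day 45 visit (Section 6.0), ±2 days: Day 43 to Day 47.
- Overlap: Day 43, 44 and 45 = 3 days, on which the visit can be handled as End of Study under the exemption.
- Remainder: 11 − 3 = 8 days (Day 35–42), on which footnote P is the only applicable rule.

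The documents give no reaction or termination rates, so no expected number of patients can be calculated. About 20 patients are planned.

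**The case against.** The strongest reply is that the rules can be read together without conflict. Footnote l names no visit. Footnote f imports the End of Study challenge, which is already conditional, and footnote P then only narrows when that challenge carries over. The protocol also uses unqualified mandatory wording elsewhere. Sections 4.2 and 6.1.1 both schedule a Day 45 challenge without mentioning the exemption, and both plainly give way to it.

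An Investigator could reasonably reach that reading, but it does not remove the gap. Sections 4.2 and 6.1.1 give way because other text states the exemption for Day 45 expressly. No text states it for the ET visit. A site that skipped the challenge on this reasoning would be departing from footnote P as written.

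Three further points stand and limit the finding:
- Amendment 5's entry for Table 4.1 covers the table as a whole, so the log cannot show that footnote P in particular was overlooked. The current footnote still lacks the exemption.
- The placement of footnote letters in Table 4.1 is unreliable in the available text, so nothing here rests on which cells carry footnote l.
- The practical risk is small. Every enrolled patient has already reacted at screening, and the plan allows reactors to be challenged again at Day 45. Section 6.1.1 provides that "At the first sign of an objective allergic reaction, the challenge will be stopped". Patients may withdraw at any time under Section 4.3.5, so no one can be made to take the challenge.

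**Conclusion.** The point holds, as a minor safety inconsistency. As written, footnote P directs a final challenge in Day 14/15 reactors who leave on Day 35–45 for non-medical reasons, while the plan makes that challenge optional for reactors at Day 45. The contrast is between *will* and *may*; the challenge is not prohibited in these patients anywhere.

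It would affect few patients and possibly none. It needs a Day 14/15 reactor, a non-medical termination on about Day 35–42, and a patient willing to return. The conclusion assumes that footnote P, as the specific ET rule, prevails over the general footnote f. The primary Day 14 analysis is untouched, and no bias is claimed in the exploratory Day 45 analysis.

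**What to change.** Add one clause to footnote P and mirror it in Section 6.2.6: *except that for a patient with an objective reaction at Day 14/15 this challenge is optional and the Investigator decides whether to do it, as in Section 6.2.5.*

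This takes a short protocol amendment. It adds no procedure and no patients, and the Investigator can still choose to challenge. The only loss is an occasional exploratory challenge value from an ET visit.

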## 4.2 Discussion of Study Design

ANB020 is a first-in-class, anti-IL-33 therapeutic antibody developed by AnaptysBio, to treat Th2 cell driven inflammatory diseases with underlying IL-33 dysregulation. Preliminary evidence of this compound's significant PD activity in terms of cytokine modulation has been demonstrated in non-clinical and clinical studies, justifying its further development in patients with AD. Emergent data of the Phase I study (ANB020-001) in healthy subjects are the basis for the dose and IV route of administration of ANB020. The 300 mg IV dose was found to be safe and well tolerated in healthy subjects. The SAD part of the study has been completed but the MAD part of the study is ongoing. In the SAD part of the study, 64 subjects were enrolled and dosed. The doses implemented in the SAD study were 10, 40, 100, and 300 mg SC and 40, 100, 300, and 750 mg IV. No change in vital signs (BP, HR, ECG, or body temperature) was noted. Hematology parameters, such as erythrocytes, WBC and platelet counts, were all within the normal range except for one subject in the 750 mg dose group. All others did not show any modification or trend related to ANB020 administration. Serum chemistry results were also all in the normal range. The most commonly reported TEAEs were upper respiratory tract infection (50% versus 48% in placebo and ANB020 group, respectively) and headache (32% versus 27% in placebo and ANB020 group, respectively) of mild to moderate intensity. No AEs were deemed by the PI to be related to ANB020. Of all the AEs reported across all dose groups, 44% were reported as possibly related and 36% were reported as unrelated. One SAE of decreased neutrophils was reported in the 750 mg dose group which resolved without sequelae prior to study completion. No other observations of decreased neutrophils were observed. No dose dependent AEs were reported.

The dose of ANB020 selected for this study 300 mg/100 mL (IV) has provided complete inhibition of IL-33 induced cytokine release (ex vivo) up to 43 days and has been administered safely in study ANB020-001.

Patients with food allergy must consistently avoid food allergens including that which is often not readily apparent from visual inspection (cross-contamination during preparation or serving of food), to prevent potentially life threatening reactions. These avoidance measures significantly affect their quality of life. There are no currently approved treatments to prevent reactions from accidental ingestions. The use of targeted immune modulators such as ANB020 may be able to reduce the Th2 specific inflammatory cascade that trigger the clinical symptoms of a reaction. Other monoclonal Th2 immune modulators such as anti-IgE have shown promising but inconsistent results in clinical studies.

This is a proof of concept study aiming to assess the effects of ANB020 compared to placebo in patients with peanut allergy and provide evidence that the hypothesized mechanisms is

affected by the IP and that the effect on the mechanism leads to a desired short-term clinical outcome such as increased tolerance to food peanut antigen challenge.

This study uses a screening BPCFC to provide a baseline for the assessments performed after ANB020 or placebo administration. Patients will receive active ANB020 or placebo in a 3:1 ratio on Day 1. On Day 14 and on Day 45, the oral BPCFC will be administered again. The BPCFC may be split into 2 days if the Investigator feels that that it is the best for patient's safety and convenience. Patients will be followed after ANB020 administration for PK, PD, and safety assessments from a single dose.

### **4.3 Selection of Study Population**

Eligibility criteria for this study have been carefully considered to ensure the safety of the patients included in the study and that the results of the study can be used. It is imperative that patients fully meet all of the inclusion criteria and none of the exclusion criteria.

#### **4.3.1 Inclusion Criteria**

Patients will be enrolled in the study only if they meet all of the following criteria:

- Male and female patients with age >18 years and able to give informed consent.
- Patients with a confirmed clinically allergic response to peanut.
- Positive clinical reaction observed during the peanut oral food challenge and no clinical reaction observed during the placebo challenge.
- Positive peanut allergy skin prick test >3 mm of the negative control and detectable serum peanut-specific IgE levels (>0.35 kU/L) by ImmunoCAP testing. Skin prick test and ImmunoCAP testing will be conducted only if these tests had not been performed within 8 weeks before screening.
- Body mass index (BMI) of 18 to 36 kg/m^2 (inclusive) and total body weight >50 kg (110 lb). BMI = weight (kg)/(height [m^2]).
- Willing and able to comply with the study protocol requirements.
- Have the ability to read and understand the study procedures and have the ability to communicate meaningfully with the Investigator and staff.
- Women of childbearing potential, must have a negative serum pregnancy test at screening and Day 1, and be surgically sterile or using an acceptable method of contraception throughout the study and for 15 weeks after the last administration of IP. Postmenopausal patients defined as (1) aged over 45 years with at least 1 year of amenorrhea and levels of

follicle stimulating hormone (FSH) over 20 IU/L at screening or (2) aged over 50 years with at least 1 year of amenorrhea.

- Male patients must be willing to use effective methods of contraception during the entire study period and for 15 weeks after the last administration of IP (See [Section 4.3.4](#)).

#### **4.3.2 Exclusion Criteria**

Patients will not be enrolled in the study if they meet any of the exclusion criteria:

- Have concomitant dermatological or medical condition(s) which may interfere with the Investigator's ability to evaluate the patient's response to the IP.
- Have experienced severe life-threatening anaphylactic reactions to peanuts within 6 months before screening (i.e., requiring an intensive care unit (ICU) admission).
- Positive clinical reaction observed during the placebo oral food challenge.
- Participation in any interventional study for the treatment of peanut and/or food allergies in the 12 months before screening.
- Have received any IP or been part of any interventional clinical study within a period of 3 months or 5 half-lives (whichever is longer) before screening.
- Have received systemic corticosteroids, nonsteroidal, immunosuppressant, or immunomodulating drugs treatments within 2 weeks before screening.
- Use of beta blockers, angiotensin-converting enzyme inhibitors, angiotensin-receptor blockers, or calcium channel blockers within 2 weeks before screening.
- History of ischemic cardiovascular diseases.
- Use of biologics such as omalizumab within 6 months before screening or subject is in build-up phase of allergen immunotherapy (excluding peanut) and has not reached maintenance dose.
- Have received antibiotic treatment within 1 week before screening.
- Have a history of hypersensitivity or allergic reactions following infusions of human blood or blood components.
- Have a history of hypersensitivity or allergic reactions to polysorbate 80 a component of ANB020 formulation or the inactive ingredients (excipients).
- If female, are pregnant or lactating, or intend to become pregnant during the study period.

- Current diagnosis of asthma requiring Global Initiative for Asthma Assessment (GINA) Step 4 or higher treatment or asthma partially controlled or uncontrolled according to GINA classifications in the last three months before screening ([Appendix I](#)).
- History of a life threatening asthma attack within 1 year before screening (example: requiring an ICU admission, intubation with mechanical ventilation).
- Other significant medical conditions that in the opinion of the PI, prevent participation in the study
- History of drug, alcohol or other substance abuse, or other factors limiting the ability to cooperate and to comply with the study protocol.
- Have any other physical, mental, or medical conditions which, in the opinion of the Investigator, make study participation inadvisable or could confound study assessments.
- Receipt of a live attenuated vaccine within 4 weeks before screening.
- Planned surgery during the study or 30 days before screening.

#### **4.3.3 Disease Diagnostic Criteria**

Adult patients (age >18 years) with a confirmed clinical peanut allergy with a positive skin prick test >3 mm compared to the negative control and detectable serum IgE antibodies to peanuts (>0.35 kU/L).

#### **4.3.4 Patient Restrictions**

The following restrictions may affect patient participation in this study:

- Availability to attend visits according to the protocol.
- Concomitant medication restrictions as described in [Section 5.8](#) and medications that should be avoided prior to BPCFC as shown in [Appendix III](#).
- Women of childbearing potential must use a double-barrier method of contraception during the study (45 days) and for 15 weeks after the last administration of IP. Male patients must use effective methods of contraception (total abstinence or condom with spermicide) during the study and for at least 15 weeks after the last administration of IP. For woman of childbearing potential, abstinence alone is not an acceptable method of contraception.
- Restricted alcohol intake (<28 units per week) (1 unit of alcohol is equivalent to 8 ounces of beer, 4 ounces of wine, or 1 ounce of spirits).
- Strenuous exercise should be avoided up to 72 hours before planned study visits.

